## 9.4 STATISTICAL ANALYSES

The primary analysis is planned when the last patient randomized reaches Day 29 (or planned Day 29 if the patient is discharged or leaves the study early). Final analysis will be performed at study end (ie, Day 60).

The SAP will be finalized prior to the interim analysis and it will include a more technical and detailed description of the statistical analyses described in this section. This section is a summary of the planned statistical analyses of the most important endpoints including primary and key secondary endpoints.

### 9.4.1 General considerations

For continuous variables, descriptive statistics will include the following information: the number of patients reflected in the calculation (n), mean, standard deviation, Q1, median, Q3, minimum, and maximum.

For categorical or ordinal data, frequencies and percentages will be displayed for each category.

Subgroups will be defined by key baseline factors (eg, demographics, disease characteristics). Subgroup analyses will be performed on efficacy endpoints and safety endpoints, as needed. Details will be described in the SAP.

Statistical analyses will be performed using Statistical Analysis Software (SAS) version 9.4 or higher.

#### **9.4.2 Primary endpoint(s)**

The primary endpoint is the time to improvement of 2 points in clinical status assessment from baseline using the 7-point ordinal scale. Patient who discharged early will be considered as meeting the two points improvement criteria.

The primary endpoint will be analyzed using a log-rank test stratified by randomization stratum with treatment as a fixed factor in the mITT population. P-value for the pairwise treatment comparison versus placebo will be provided. Estimation of treatment effect of each sarilumab dose will be provided as hazard ratio (sarilumab versus placebo) using Cox proportional hazards model stratified by the randomization stratum with treatment as a covariate, along with 2-sided confidence intervals. Kaplan-Meier (KM) plot and the median time-to- improvement of 2 points will also be provided.

Superiority of sarilumab over placebo will be declared if the null hypothesis is rejected at the 5% (2-sided) significance level following the multiplicity control procedure specified in [Section 9.4.3.1](#).

Patients who have an improvement of 2-points in clinical assessment or discharge will be considered as events, while patients who do not experience improvement of 2-points will be censored at the last observation time point. Patients who die or take rescue medication in the study without improvement of 2-points before that will be censored at the earlier date of Day 29 (for the primary analysis) or rescue medication started.

#### **9.4.3 Secondary endpoint(s)**

##### **9.4.3.1 Efficacy**

###### **Analysis for Key Secondary Endpoint:**

The key secondary endpoint is the percent of patients alive at Day 29.

The key secondary endpoint will be analyzed using a Cochran-Mantel-Haenszel (CMH) test stratified by randomization stratum in the mITT population. Estimation of treatment effect of each sarilumab dose will be reported as difference in proportion of patients alive at Day 29 (sarilumab - placebo), along with 95% confidence levels. P-value for the pairwise treatment comparison versus placebo will be provided.

Superiority of sarilumab over placebo will be declared if the null hypothesis is rejected at the 5% (2-sided) significance level following the multiplicity control procedure specified in [Section 9.4.3.1](#).

###### **Analysis for Other Secondary Endpoints:**

- Differences in time-to-event endpoints by treatment will be summarized with Kaplan-Meier estimates and 95% confidence intervals.
- Change in ordinal scale at specific time points will be summarized by proportions (eg, proportion who have a 1-, 2-, 3-, or 4-point improvement or 1-, 2-, 3-, 4-point worsening).

- Duration of event (eg, duration of mechanical ventilation) will be summarized according to median days with quartiles.
- Incidence data (eg, incidence of new oxygen use) will be summarized as a percent with 95% confidence intervals.
- Continuous endpoints and their changes from baseline will be summarized through descriptive statistics including mean, standard deviation, median and quartiles, and 95% confidence intervals of means, as needed.
- Categorical data (eg, ordinal scale by day) will be summarized according to proportions with confidence intervals on the difference or odds ratios for a binary or multiple category scale, respectively.

Missing data procedures will be described in the SAP.

### **Control of multiplicity**

Multiplicity will be controlled for the primary analysis (i.e. Day 29), final analysis (i.e. Day 60) will be supportive.

For the primary and key secondary endpoints, multiplicity will be controlled via a hierarchical testing procedure in the following order:

1. Primary endpoint sarilumab 400 mg versus placebo
2. Key secondary endpoint sarilumab 400 mg versus placebo
3. Primary endpoint sarilumab 200 mg versus placebo
4. Key secondary endpoint sarilumab 200 mg versus placebo

If one sarilumab dose is discontinued for safety reasons, then all comparisons versus placebo for that dose will be removed and the remaining comparisons will be tested in the order specified above.

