#### Protocol amendment summary of changes table

Section # and Name	Description of Change	Brief Rationale
Section 1.1 Synopsis, Section 1.2 Schema, Section 2.1 Study Rationale, Section 4.1 Overall Design, Section 4.2 Scientific Rationale for Study Design, Section 4.3 Justification for Dose, Section 6.1. Study Interventions administered (Table 3)	Closed enrollment to the sarilumab 200 mg IV arm	Based on anticipation of a more favorable benefit-risk profile in the 400 mg arm versus the 200 mg arm, enrollment in the 200 mg arm will be closed upon implementation of amended protocol 04.

Section # and Name	Description of Change	Brief Rationale
Section 1.3 Schedule of Activities	Urinalysis and urine culture results, serum IL-6, adverse events	The timing of urinalysis, urine culture results, serum IL-6, and adverse events assessments was clarified. No changes were made to the collection schedule.
Section 5.2	E04 was modified to clarify that oral corticosteroids were a type of systemic corticosteroids.	Clarification of definition.
Section 10.3.1 Definition of AE	Events meeting the AE definition: Removed: "Lack of efficacy" or "failure of expected pharmacological action" per se will not be reported as an AE or SAE. Such instances will be captured in the efficacy assessments. However, the signs, symptoms, and/or clinical sequelae resulting from lack of efficacy will be reported as AE or SAE if they fulfil the definition of an AE or SAE.	This bullet is duplicated in error. The same information is included in the first bullet.
Section 10.3.1 Definition of AE	Events meeting the AE definition: The signs, symptoms, and/or clinical sequelae resulting from lack of efficacy will be reported as AE or SAE if they fulfil the definition of an AE or SAE. Also, "lack of efficacy" or "failure of expected pharmacological action" also constitutes an AE or SAE.	This bullet is contradictory to the information provided, stating "Lack of efficacy" or "failure of expected pharmacological action" per se will not be reported as an AE or SAE.
Section 10.3.2.1 Recording and follow-up of AE and/or SAE	Added tables for assessment of intensity for infusion related reactions, hypersensitivity reactions, and neutropenia. Added guidance for the follow-up of AESIs of ALT increase and Grade 4 Neutropenia.	Provide guidance to the investigator.

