If one sarilumab dose is discontinued for safety reasons, then all comparisons versus placebo for that dose will be removed and the remaining comparisons will be tested in the order specified above.

An interim analysis is planned to be performed when approximately 50% of total planned number of patients (~200) are randomized. The purpose of the interim analyses is to obtain an understanding of the possible drug effect in the population under study. An administrative alpha of 0.001 will be spent at interim analysis (1).

[figure not shown]
The interim analyses will be performed by an external statistical analysis center and are separated from personnel involved in the trial conduct. The unblinded results can only be viewed by a small group of senior sponsor individuals, who are separate from sponsor personnel involved in the conduct of the study. People involved in the conduct of the study (Patients, Investigators, Study Team, and Project Team) will have no access to the interim analysis results.

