## 4 STUDY DESIGN

### 4.1 OVERALL DESIGN

This study is an adaptive phase 3, randomized, double-blind, placebo-controlled trial to evaluate the efficacy and safety of sarilumab in hospitalized adults with severe or critical COVID-19. The study will be conducted in Europe and other countries except in the United States (US) in up to 100 sites.

Patients will be randomized in a 2:2:1 allocation ratio to sarilumab 400 mg IV, sarilumab 200 mg IV, or placebo. The sarilumab 200 mg IV dose arm will be closed for patients enrolled after Amended Protocol 04 is implemented. Patients enrolled after implementation of Amended Protocol 04 will be randomized in a 2:1 allocation ratio to sarilumab 400 mg IV or placebo (Section 4.3). All patients will receive a single dose of study drug on Day 1. Patients may receive a second dose with study drug (based on the original treatment group assigned) 24 to 48 hours after the first dose, if

1. The Benefit Risk assessment by the investigator favors the administration of another dose of study drug without compromising safety (e.g., increase in LFTs, neutropenia)

AND

2. At least one of the following criteria is met:
  - Increase in fever or recurrence of fever compared to Day 1 OR
  - Increase or no change in FiO2 requirement compared to Day 1 OR
  - Requiring vasopressors, ECMO, or development of multi-organ dysfunction

The safety data from approximately the first 12 patients randomized (assuming a total of ~10 patients are dosed on the sarilumab doses of 200 mg IV or 400 mg IV) will be reviewed by an independent data monitoring committee (IDMC) after the last of these patients dosed reaches Day 7. Data on approximately the first 12 and 50 patients (regardless of severity of illness) with at least 7-days follow-up will be reviewed by the IDMC to determine if the study can continue with or without modification. Subsequently, the frequency of IDMC meetings will be determined following the first 2 IDMC meetings. In addition to these specific assessment times, the IDMC will actively monitor interim data to make recommendations about early study closure, changes to study arms, and/or the eligible patient population throughout the course of the study.

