Senior management, who are separate from the blinded team involved in study management and are not involved in any study related activities, reviewed a pre-specified, one time, unblinded interim analysis report ([Section 9.5](#)). Subsequent to this review, a scheduled IDMC reviewed additional unblinded data that is not available to this senior management team ([Section 9.6](#)). Both groups suggested to stop enrollment in the 200 mg arm. Thus, based on anticipation of a more favorable benefit-risk profile in the 400 mg arm versus the 200 mg arm, enrollment in the 200 mg arm will be closed upon implementation of amended protocol 04. The ratio of 2:1 will continue to be maintained for sarilumab 400 mg IV versus placebo after Amended Protocol 04 is implemented.

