### Study Level Stopping Rules

An independent data monitoring committee (IDMC) will actively monitor the ongoing safety of patients and can make recommendations about early study closure or changes to the conduct of the study. The Sponsor may decide to stop or make changes to the study based on the recommendations of the IDMC.

A treatment arm may be discontinued if there is a clinically meaningful imbalance between treatment arms in any of the following safety criteria:

1. Incidence of SAEs
2. Incidence of AESIs
3. Progression of COVID-19 to more severe, critical or multi-organ dysfunction
4. Incidence of clinically significant recurrence of severe or critical disease after clinical improvement

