2.4.4.3 Multiplicity issues

Multiplicity will be controlled for the primary analysis (ie, Day 29). Final analysis (ie, Day 60) will be supportive.

For the primary and key secondary endpoints, multiplicity will be controlled via a hierarchical testing procedure in the following order:

1. Primary endpoint sarilumab 400 mg versus placebo
2. Key secondary endpoint sarilumab 400 mg versus placebo
3. Primary endpoint sarilumab 200 mg versus placebo
4. Key secondary endpoint sarilumab 200 mg versus placebo

If one sarilumab dose is discontinued for safety reasons, then all comparisons versus placebo for that dose will be removed and the remaining comparisons will be tested in the order specified above.

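### After Amendment 04 closes the 200 mg arm, the testing hierarchy still compares 200 mg with the whole placebo group, including placebo patients randomised after closure

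*Protocol*

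**What the plan says.** Protocol Section 4.1 sets 2:2:1 allocation up to Amendment 04. After that, "Patients enrolled after implementation of Amended Protocol 04 will be randomized in a 2:1 allocation ratio to sarilumab 400 mg IV or placebo". The Amendment 04 change table records "Closed enrollment to the sarilumab 200 mg IV arm" for Sections 1.1, 1.2, 2.1, 4.1, 4.2, 4.3 and 6.1. Section 9 is not among them.

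The current Synopsis and Section 9.4.3.1 keep a four-step hierarchy: primary then key secondary endpoint for 400 mg, followed by "Primary endpoint sarilumab 200 mg versus placebo" and the key secondary endpoint for 200 mg. Sections 9.4.2 and 9.4.3.1 specify a stratified log-rank test and a stratified CMH test in the mITT population. Table 10 defines that population as every randomised and treated patient. The strata are severity and systemic corticosteroid use. There is no calendar term and no restriction to concurrent placebo.

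On removing a dose, the Synopsis says "If one sarilumab dose is discontinued for safety reasons, then all comparisons versus placebo for that dose will be removed". Section 9.4.3.1 has the same rule, and SAP 2.4.4.3 opens its version with "If one sarilumab dose is discontinued for safety reasons". The reason for closure in Section 4.3 is "based on anticipation of a more favorable benefit-risk profile in the 400 mg arm versus the 200 mg arm". Of senior management and the IDMC it says "Both groups suggested to stop enrollment in the 200 mg arm". Section 7.2 says "A treatment arm may be discontinued if there is a clinically meaningful imbalance between treatment arms in any of the following safety criteria".

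SAP version 2 (05-May-2020) follows Amendment 03. Amendment 04 is dated 11-Jun-2020, so the SAP needs updating but is not itself in error.

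**The concern.** There are two gaps.

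First, the control group. Placebo patients randomised after closure had no chance of receiving 200 mg, so comparing them with the 200 mg arm is not a randomised comparison. Stratification absorbs a changing mix of severity or baseline corticosteroid use, but not a change in outcome within strata over calendar time. The protocol itself stresses, in Section 4.2, that knowledge of disease course was still evolving. If later placebo outcomes are worse, 200 mg looks falsely superior. If they are better, 200 mg can look falsely harmful.

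Second, the status of the tests. The removal rule is tied to safety, while the stated reason is anticipated benefit-risk. A reader cannot tell whether steps 3 and 4 remain confirmatory.

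Even if they drop out, Sections 9.4.2 and 9.4.3.1 still promise a 200 mg hazard ratio, survival difference and p-values, and these carry the same bias.

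**Working it through.** **1. The plan's own power figure.** With exponential times, the rate ratio from 45% and 70% at Day 15 (Section 9.2) is ln(0.30)/ln(0.55) = 2.01. By Day 29 the event proportions are 1 − 0.55^(29/15) = 0.685 for placebo and 1 − 0.30^(29/15) = 0.9025 for sarilumab. The expected events are 80 × 0.685 + 160 × 0.9025 = 199. Schoenfeld: √(199 × 2/9) × ln 2.01 − 1.96 ≈ 2.70, a power of 99.7%. The stated minimum of 90% is reproduced.

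**2. Arm sizes if closure comes after N₀ of 400 randomised.** N₀ is not in the documents and is assumed. The 200 mg arm has 0.4N₀, concurrent placebo 0.2N₀ and later placebo (400 − N₀)/3.

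| N₀ | 200 mg | Concurrent placebo | Later placebo | Later share |
|---|---|---|---|---|
| 200 | 80 | 40 | 67 | 63% |
| 300 | 120 | 60 | 33 | 36% |
| 360 | 144 | 72 | 13 | 16% |

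The earliest possible point is 200, because the interim report that preceded closure is triggered there (Section 9.5). At the planned accrual of 400/90 = 4.44 per day, 300 and 360 come about 22 and 36 days later. These are more plausible. At 45 days enrolment is complete and the issue disappears.

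**3. Step 3 with no 200 mg effect.** Daily log-rank to Day 29, hazard −ln(1 − p)/15, 40,000 runs per cell. False superiority means Z > 1.96 (nominal 2.5%). The drift sizes are assumptions.

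| Placebo Day 15 rate | 200 | 300 | 360 |
|---|---|---|---|
| No drift | 2.7% | 2.4% | 2.4% |
| Abrupt 45% to 40% at closure | 7.9% | 4.9% | 3.3% |
| Abrupt 45% to 35% at closure | 20% | 9.7% | 4.6% |
| Linear 45% to 40% over the trial | 4.8% | 3.4% | 2.8% |
| Linear 45% to 35% over the trial | 8.1% | 4.9% | 3.2% |

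The abrupt fall to 35% gives a spurious hazard ratio of 1.23, 1.12 or 1.05. An abrupt rise to 55% gives two-sided rejection of 17.5%, 9.4% or 5.8%, almost all against 200 mg.

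**4. What the strata absorb.** Assume Day 15 rates of 60% in severe and 30% in critical patients, mixed 50:50 before closure, with a log-rank stratified by severity. Drift in severity mix alone is fully absorbed (2.3–2.6%). Within-stratum drift to an overall 40% gives 8.3%, 5.1% and 3.3%. Drift to 35%, half from mix and half within strata, gives 8.2%, 5.3% and 3.2%. A separate simulation stratified by both factors (2,000 runs) gave 20.3% at N₀ = 200 and 8.5% at 300 for a 10-point fall.

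**5. The gate.** Step 3 opens only after steps 1 and 2. Take 400 mg at the planned ratio of 2.01 and assumed Day 29 survival of 90% or 93% against 85%, independent of improvement. Steps 1 and 2 are then both passed in 26/25/23% or 61/57/52% of trials. False superiority at step 3 jointly with the gate is 2.2–4.9%, 1.2–2.7% and 0.8–1.7% for the abrupt fall to 40%. For the fall to 35% it is 5.3–12.3%, 2.4–5.6% and 0.9–2.5%.

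**6. Step 4.** Suppose placebo survival is 85% before closure and 80% after, with no 200 mg effect. The bias is the later share × 5 points: 3.1, 1.8 and 0.8 points. A pooled two-proportion test (400,000 runs) gives marginal false superiority of 7.7%, 5.0% and 3.8%. Jointly with step 2, taking step 3 as passed, it is 5.4–7.3%, 3.7–4.8% and 2.9–3.7%. Linear drift from 85% to 80% gives 4.3%, 3.5% and 3.1% marginally.

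**7. Concurrent placebo only.** Two-sided error is 4.7–5.4% in every cell, and joint false superiority at step 4 is 1.7–2.7%.

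**The case against.** The strongest case against concerns size. Enrolment was already rapid by 08-Apr-2020 (Amendment 02 rationale), and Amendment 04 is dated 64 days after that and 85 days after the 18-Mar-2020 protocol. At 4.44 per day that is about 284 to 378 randomised, so roughly 41% down to 9% of placebo would be non-concurrent. Closure takes effect only on implementation, which lowers the share further. For closure at 284 to 378, joint false superiority at step 3 is 0.6–2.1% for linear drift to 40%, 0.6–3.2% for linear drift to 35%, and 0.7–3.3% for an abrupt fall to 40%. Clear inflation, up to 6.7%, needs an abrupt 10-point within-stratum fall with closure near 284–300. Drift size and direction are assumed, and improving outcomes would not produce a false claim of superiority.

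It can also be argued that the removal rule already disposes of steps 3 and 4: benefit-risk includes risk, and the listed grounds for discontinuing an arm are safety criteria. Section 9 is described as a summary, so it is silent on the placebo group rather than explicit.

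Most of this stands as a limit on magnitude. It does not supply the missing rule. The text still supports two readings of the removal clause, no section names the placebo group for 200 mg, and the gate does not protect the 200 mg estimates and p-values, which are reported in any case.

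**Conclusion.** The concern holds. On the current text the 200 mg comparisons include placebo patients randomised after closure, and whether those comparisons remain confirmatory is undecided.

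Without within-stratum drift the error rate is unaffected. With it, the bias can run either way. At the more plausible closure points of 300 and 360, abrupt falls of 5 to 10 points give marginal false superiority of roughly 3% to 10% at step 3. The joint rate after the gate is often near or below 2.5%. The figures for closure at 200 are an upper bound, not an expectation. All of them rest on assumed closure counts, drift and 400 mg survival.

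Steps 1 and 2 are untouched, because 400 mg and placebo are randomised 2:1 throughout. This is an inexpensive repair to the analysis of a closed dose, worth making because it removes a known bias and a later choice of control group. It does not threaten the lead comparison.

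**What to change.** The blinded team should settle two points before unblinding for the primary analysis.

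1. In the Synopsis, Section 9.4.3.1 and SAP 2.4.4.3, state whether the 200 mg steps stay in the hierarchy or become descriptive after this closure, and reconcile the removal rule with the reason given in Section 4.3.
2. In the Synopsis, Sections 9.4.2 and 9.4.3.1, and SAP 2.4.4.1 and 2.4.4.2, add wording such as:

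> All sarilumab 200 mg versus placebo comparisons include only patients randomised while 200 mg was an available allocation in the IRT (determined per site if implementation is site by site). The same comparison with all placebo patients is a sensitivity analysis. Sarilumab 400 mg versus placebo uses all placebo patients.

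The cost is protocol and SAP wording, one analysis flag from the IRT, and a smaller placebo group for the closed arm. At the planned 45% versus 70%, simulated power with concurrent placebo is 89% (80 v 40), 97% (120 v 60) and 99% (144 v 72). With all placebo and no drift it is 98.9%, 99.5% and 99.6%. Only closure at 200 falls marginally below the planned 90%.

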### **9.4.3.2 Safety**

#### **9.4.3.2.1 Adverse events**

Definitions

For safety variables, the following observation period is defined:

The on-treatment period is defined as the day from first dose of study drug to the last dose of study drug plus 60 days.

Treatment-emergent adverse events (TEAEs) are defined as those that are not present at baseline or represent the exacerbation of a pre-existing condition during the on-treatment period.

In addition, there will be an end of study (EOS) phone call follow-up to determine the vital status (alive or dead) of the patient and to assess for SAEs and AESI.

## Analysis

All AEs reported in this study will be coded using the currently available version of the Medical Dictionary for Regulatory Activities (MedDRA®). Coding will be to lowest level terms. The preferred term (PT), and the primary system organ class (SOC) will be listed.

Summaries of all TEAEs by treatment group will include:

- The number (n) and percentage (%) of patients with at least 1 TEAE by SOC and PT
- TEAEs by severity, presented by SOC and PT
- TEAEs by relationship to treatment (related, not related), presented by SOC and PT
- Treatment-emergent AESIs (defined with a PT or a prespecified grouping)

Deaths and other SAEs will be listed and summarized by treatment group.

Treatment-emergent adverse events leading to permanent treatment discontinuation will be listed and summarized by treatment group.

